1.3.1. Dose administration schedule and escalation

The initial schedule (see [Figure \(1.3.2\) 1](#)) will consist of a lead-in period followed by 28-day cycles when S64315 will be administered in combination with azacitidine. S64315 will be administered via intravenous (IV) infusion over at least 2 hours once every week, azacitidine will be administered via subcutaneous (SC) injection once daily for 7 consecutive days.

The schedule will be as follows:

- A 2-week LID period with S64315 fixed LID1 of 25 mg on day -13 (D-13) and S64315 fixed LID2 of 50 mg on D-6, followed by

- 28-day cycles (Cx) of combination treatment period with S64315 administered on CxD2, CxD9, CxD16 and CxD23, and 75 mg/m² of azacitidine administered daily for 7 days from CxD1 to CxD7 followed by a rest period of 21 days.

On days of concomitant administration of S64315 and azacitidine (CxD2), azacitidine should be administered 2 hours (± 10 min) prior to S64315. The starting dose of S64315 after the lead-in period will be 50 mg. A panel of doses (see [Table \(1.3\) 1](#) from 25 mg (-1) and up to 250 mg could be explored according to the dose escalation process of the Bayesian Logistic Regression Model (BLRM).

During the dose escalation phase, at each new dose level, the IMPs will be firstly administered to one patient. If no medically important or life-threatening toxicity occurs during a 1 week observation period, the subsequent patients will be allowed to start treatment without further delays between subsequent patients. The dose increase between two dose levels will be guided by the observed toxicities.

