4.2.1.5. Extent of exposure and treatment compliance

Global treatment duration

Global treatment duration (weeks) is defined as $(\min [\max (\text{last intake date of the last cycle azacitidine} + 21 \text{ days, last intake date of S64315} + 6 \text{ days), death date, withdrawal date}] - \text{first IMP intake} + 1) / 7$.

Treatment duration for S64315 including LID period (QW)

Treatment duration (days) for S64315 is defined as $[(\min (\text{last infusion date} + 6 \text{ days, death date, withdrawal date}) - \text{first S64315 infusion date}) + 1]$.

Treatment duration (weeks) for S64315 is defined as $[(\min (\text{last infusion date} + 6 \text{ days, death date, withdrawal date}) - \text{first S64315 infusion date}) + 1] / 7$.

Treatment duration for S64315 excluding LID period (QW)

Treatment duration (days) for S64315 is defined as $[(\min (\text{last infusion date} + 6 \text{ days, death date, withdrawal date}) - \text{first S64315 infusion date of cycle 1}) + 1]$.

Treatment duration (weeks) for S64315 is defined as $[(\min (\text{last infusion date} + 6 \text{ days, death date, withdrawal date}) - \text{first S64315 infusion date of cycle 1}) + 1] / 7$.

Treatment duration for azacitidine

Treatment duration (days) for azacitidine is defined as $[\min (\text{last intake date of the last cycle} + 21 \text{ days, death date, withdrawal date}) - \text{first azacitidine intake} + 1]$.

Treatment duration (weeks) for azacitidine is defined as $[\min (\text{last intake date of the last cycle} + 21 \text{ days, death date, withdrawal date}) - \text{first azacitidine intake} + 1] / 7$.

S64315 treatment duration in LID period:

S64315 treatment duration in LID period LID(days) is defined as $[\min (\text{first S64315 infusion date of cycle 1-1, death date, withdrawal date}) - \text{first S64315 infusion date of LID1}] + 1$.

Note: In case of missing first S64315 at cycle 1, S64315 treatment duration in LID period is defined as $[\min (\text{last S64315 infusion date in LID} + 6, \text{ death date, withdrawal date}) - \text{first S64315 infusion date of LID}] + 1$. LIDLID

LID period duration (weeks): LID period duration (days) / 7.

Cycle duration for S64315

Duration of cycle i (weeks) for S64315 is defined as $[\text{first IMP intake of cycle } (i+1) - \text{first IMP intake of cycle } i] / 7$.

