Note: The duration of the last cycle for S64315 will be estimated to be 4 weeks for the calculation of dose intensity and relative dose intensity at the last cycle.

Cycle duration for azacitidine

Duration of cycle i (weeks) for azacitidine is defined as [first IMP intake of cycle $(i+1)$ – first IMP intake of cycle i] / 7.

Of note,

- The duration of the last cycle for azacitidine will be defined as [(last intake of last cycle + 21 days) – first intake of last cycle + 1] / 7.

Numbers of cycles for S64315/azacitidine

The number of cycles with study drug intake for S64315/azacitidine will be defined based on patient exposure data while on treatment excluding S64315 LID period. A patient is considered to enter in a cycle if there is at least one intake date.

Real administrated dose of S64315 will be recorded directly from S64315 infusion e-CRF page. For information, the administrated dose is recorded in mL within e-CRF. The conversion of the real administrated dose in mg is directly calculated by the data manager. Little variation between planned dose and real administrated dose can be expected due to feasibility (IMP preparation and injection).

Planned dose intensity (PDI) for S64315 (mg/week)

Planned dose intensity (PDI) for S64315 (mg/week)	Schedule (QW)
	4 intakes per cycle / 1 intake per LID week
Dose Level -1: 25 mg*	25 mg/ week*
Dose Level 1: 50 mg**	50 mg/ week**
Dose Level 2: 100 mg	100 mg/ week
Dose Level 3: 200 mg	200 mg/ week
Dose Level 4: 250 mg	250 mg/ week

* LID1 dose.

** LID2 dose

However, it is possible that intermediate or higher dose levels are added during the course of the study.

Cumulative dose for S64315

The cumulative dose (mg) for S64315 per patient in a time period (during the treatment period including LID or per cycle) is the sum of the total dose levels that the patient received within that period according to the compliance.

$$\text{Cumulative dose (mg)} = \sum_{\text{timeperiod}} (\text{Real Administrated dose (mg)}).$$

Dose intensity (DI) for S64315

The dose intensity (mg/ week) for S64315 per patient is defined as the cumulative dose (mg) received during the treatment period divided by the total treatment duration in weeks, including LID period.

$$DI \left(\frac{\text{mg}}{\text{wk}} \right) \text{ per patient} = \frac{\text{Cumulative dose (mg)}}{\text{Treatment duration (weeks)}}$$

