Planned dose intensity (day): 75 mg/m²/day (fixed).

Planned dose intensity (cycle or overall): (75 mg/m²/day (fixed) * 7) / 28.

Cumulative dose for azacitidine

The cumulative dose (mg/m²) for azacitidine per patient during a time period (during the treatment period or per cycle) is the sum of the total dose levels that the patient received between the first and last treatment intake according to the compliance.

$$\text{Cumulative dose (mg/m}^2\text{)} = \sum_{\text{timeperiod}} \left(\frac{\text{Real Administrated dose (mg)}}{\text{BSA (m}^2\text{)}} \right).$$

Dose intensity (DI) for azacitidine

The dose intensity (mg/m²/day) for azacitidine per patient is defined as the cumulative dose (mg/m²) received during the treatment period divided by the overall treatment duration of azacitidine.

$$DI \left(\frac{\text{mg/m}^2}{\text{day}} \right) \text{ per patient} = \frac{\text{Cumulative dose (mg/m}^2\text{)}}{\text{Overall treatment duration of azacitidine}}.$$

The dose intensity (mg/day) for azacitidine per cycle is defined as the cumulative dose (mg) received during the cycle divided by the cycle duration of azacitidine.

$$DI \left(\frac{\text{mg/m}^2}{\text{day}} \right) \text{ at cycle } i = \frac{\text{Cumulative dose (mg/m}^2\text{) received at cycle } i}{\text{Cycle } i \text{ duration of azacitidine}}.$$

Relative dose intensity (RDI) for azacitidine

The relative dose intensity (%) for azacitidine per patient measures the percentage of the total trial dose planned that was really administered. It is defined as the ratio of the dose intensity (mg/m²/day) to the initial planned dose intensity (mg/m²/day).

$$RDI (\%) \text{ per patient} = \frac{DI (\text{mg/m}^2/\text{day})}{\text{Planned dose intensity (mg/m}^2/\text{day)}} * 100.$$

The relative dose intensity (%) for azacitidine per cycle is defined as the ratio of the dose intensity (mg/m²/day) at cycle *i* to the planned dose intensity (mg/m²/day).

$$RDI (\%) \text{ at cycle } i = \frac{DI \text{ at cycle } i (\text{mg/m}^2/\text{day})}{\text{Planned dose intensity at cycle } i (\text{mg/m}^2/\text{day)}} * 100.$$

Treatment interruption for azacitidine

A treatment interruption is defined according to the azacitidine injection e-CRF page (Did the patient receive at least one azacitidine injection (Yes/No)).

Number of cycles with at least one treatment interruption for azacitidine experienced by a patient over the treatment period will be calculated.

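### Azacitidine RDI is divided by durations that shrink with missed first or last doses or early exit, so it overstates the share of planned dose given; only the cut at death or withdrawal lifts under-dosed patients to 100% or more

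*SAP*

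**What the plan says.** SAP 1.3.1 gives the schedule: "75 mg/m² of azacitidine administered daily for 7 days from CxD1 to CxD7 followed by a rest period of 21 days". SAP 4.2.1.5 sets the reference intensity: "Planned dose intensity (cycle or overall): (75 mg/m²/day (fixed) * 7) / 28". It describes per-patient RDI as the percentage of the planned trial dose that the patient actually received.

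The denominators come from the same section.

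- **By cycle.** An earlier cycle lasts from its first intake to the first intake of the next. The rule that opens "The duration of the last cycle for azacitidine will be defined as" yields a length in weeks, with no cut at death or withdrawal; its formula reads "last intake of last cycle + 21 days) – first intake of last cycle + 1] / 7".
- **Overall.** Per-patient dose intensity (DI) is the cumulative dose "divided by the overall treatment duration of azacitidine". The definition that starts "Treatment duration (days) for azacitidine is defined as" takes the earliest of last intake plus 21 days, death date and withdrawal date, counted from the first azacitidine intake.
- **S64315.** Here the by-cycle note differs: "The duration of the last cycle for S64315 will be estimated to be 4 weeks for the calculation of dose intensity". The note covers RDI as well, but only for that last cycle. The drug's overall treatment duration is the earliest of last infusion plus 6 days, death and withdrawal.

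SAP 3.2.5.1 tabulates azacitidine RDI overall, by cycle and per treatment period, in four classes: below 62%, 62 to below 85%, 85 to below 100%, and 100% or more.

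**The concern.** The planned intensity spreads 7 doses over 28 days, of which 21 are rest days. A denominator that drops rest days without dropping planned doses raises RDI when no extra drug was given. Both azacitidine rules can do this. One does so when the first or last doses of the final cycle are missed, the other when the patient dies or withdraws before the rest period ends.

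Dose intensity is listed among the endpoints for the primary objective (SAP 1.2), and exposure is one of the few topics that the abbreviated report keeps. The patients affected are those who stopped early, and they matter most for tolerability. The pattern is foreseeable. The first full S64315 dose is on C1D2, inside the azacitidine week, and Protocol 8.12 stops both drugs when a patient meets the S64315 discontinuation criteria.

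**Working it through.** **Inputs.** 75 mg/m² per dose, D1–D7 of 28 days (SAP 1.3.1); the formulas of SAP 4.2.1.5; the classes of SAP 3.2.5.1. Durations are taken in days except in step 5.

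**1. The plan's own reference.** Planned intensity = 75 × 7 / 28 = 18.75 mg/m²/day. With all 7 doses and no early exit, duration = 7 + 21 = 28 days, DI = 525/28 = 18.75 and RDI = 100%. The rule is right for this patient.

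**2. Last cycle, doses missed at the start or end of the week.** For k consecutive doses, duration = k + 21 days and RDI = (75k/(k + 21))/18.75 = 4k/(k + 21). The planned-dose share is k/7.

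| Doses | Days | SAP RDI | Planned-dose share |
|---|---|---|---|
| 3 | 24 | 50.0% | 42.9% |
| 4 | 25 | 64.0% | 57.1% |
| 5 | 26 | 76.9% | 71.4% |
| 6 | 27 | 88.9% | 85.7% |
| 7 | 28 | 100% | 100% |

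In a one-cycle patient only 4 of 7 changes class, from below 62% to 62–85%. The highest value with any dose missed is 88.9%. Doses missed between the first and last injection leave the denominator at 28 days.

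Over several cycles, with only the final doses of the last cycle missed and no early exit, a few overall values change class:

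- two cycles, 1 dose in the last: 64.0% against 57.1%;
- three cycles, 3 doses in the last: 85.0% against 81.0%;
- four cycles, 2 doses in the last: 86.0% against 82.1%.

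**3. Overall RDI with early exit.** In one cycle with k doses from D1 and exit on day w before last intake + 21 days, RDI = (75k/w)/18.75 = 4k/w. It is 100% or more whenever w ≤ 4k.

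- 4 doses, exit D14: 300/14 = 21.43; RDI 114.3% (share 57.1%).
- 3 doses, death D8: 225/8 = 28.125; RDI 150% (share 42.9%).
- 7 doses, exit D14: 525/14 = 37.5; RDI 200% (share 100%).
- Two cycles, 4 doses in the second, exit on its D14: 11 doses over 42 days, 44/42 = 104.8% (share 11/14 = 78.6%).
- Three cycles, same last cycle: 18 doses over 70 days, 72/70 = 102.9% (share 18/21 = 85.7%).

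**4. The two rules against each other.** The one-cycle patient with 4 doses and exit on D14 has a cycle 1 RDI of 64.0% and an overall RDI of 114.3% from the same four injections.

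**5. Units.** Azacitidine cycle duration is defined in weeks, while by-cycle DI and planned intensity are per day. Read literally, a full cycle gives (525/4)/18.75 = 700%.

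**6. S64315.** By cycle, one of four infusions in the last cycle gives 25%, as it should. Overall for the combination period, one infusion and then discontinuation gives a duration of 7 days, and so one weekly dose over one week, or 100%.

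**The case against.** The best defence is that the SAP follows one convention for both drugs: intensity over time on treatment. On that view a short denominator for a short stay is intended, and under-dosing is visible elsewhere through cumulative dose, days dosed, days at planned dose and interruption days. This stands in part. Those tables do show the shortfall, but they do not correct the RDI tables. The convention also conflicts with the SAP's own description of RDI and with a planned intensity that averages over the rest period.

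Several stronger readings are tempting, and the documents do not support them.

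- **That the last-cycle rule itself lifts under-dosed patients to 100% or more.** It adds 3 to 7 points and stops at 88.9%. Values of 100% or more with doses missed need the cut at death or withdrawal.
- **That any missed dose shrinks the denominator.** Doses missed mid-week do not.
- **That S64315 is free of the problem.** Its 4-week rule applies only by cycle; its overall duration is truncated too.
- **That the 200% example shows under-dosing.** That cycle was fully dosed; the example shows only that the denominator is wrong.
- **That DLT evaluability is affected.** It rests on dose counts (SAP 2.1), not RDI. The SAP gives no reason for the 62% and 85% cut-points, so a link to the minimum of 5 of 7 doses is inference.

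**Conclusion.** Wrong as written, in a descriptive endpoint. The by-cycle rule inflates last-cycle RDI modestly, with an occasional shift of one class. The overall rule can put a patient given about half the planned dose into the top class.

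The size of the second effect rests on an assumption: that the exit date falls before last intake + 21 days. The SAP does not define the withdrawal date. If it is the withdrawal visit, which may come up to 28 days after the last IMP dose, the cut bites only when that visit comes early. The number of affected patients therefore cannot be derived from the documents. The effect is largest with one or two cycles and dilutes as cycles accumulate.

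The weeks-against-days mismatch is a separate slip in the by-cycle formula. Nothing here bears on DLT assessment or dose escalation.

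**What to change.** In SAP 4.2.1.5, define a denominator used only for azacitidine DI and RDI, in days. Earlier cycles keep their actual interval to the next cycle. The last started cycle counts as 28 days, with no cut at death or withdrawal. Use it both by cycle and overall. One-cycle RDI then equals doses given divided by 7 (for full doses) whatever the exit day: 57.1% for 4 doses, 100% for 7.

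Leave the reported exposure durations as they are, so that a patient who died on day 8 is not credited with 28 days of treatment. Apply the same last-cycle convention to S64315 overall RDI, where the by-cycle rule already supplies it.

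The cost is a wording change and one derivation. Some reported RDIs will become lower.

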2. ANALYSIS SETS AND SUBGROUPS

2.1. Analysis sets and subgroups

- Screened Set:

All patients who signed the ICF, whether they are included or not at the end of the screening period.

- Included Set (IS):

All patients who have signed the ICF, whose eligibility was confirmed at the end of the screening period, and who were included in the dose escalation phase I part of the study.

- Safety Set (SS):

All patients who have signed the ICF and who received at least one dose of IMP (S64315 or azacitidine) during dose escalation phase I part of the study. It will be used for all safety analyses.

For the safety analysis, patients will be analysed according to the treatment combination and dose level received at C1D1 (for azacitidine) and C1D2 (for S64315). Patients who only received LID will be analysed according to the dose of S64315 planned to be administered.

- Evaluable Set (DLTES):

All patients from the SS who are evaluable for DLT according to the DLT assessment at the end of cycle 1. A patient is not considered evaluable for DLT if he/she:

- Permanently discontinued treatment before C1D28 for reasons other than DLT.
- Did not undergo a DLT assessment at the end of Cycle 1.
- Did not receive the minimum exposure criteria i.e., minimum number of doses according to the dose administration schedule of both IMPs prescribed from study entry to DLTs assessment visit (end of Cycle 1 D28), unless treatment was stopped for a DLT (see [Table \(2.1\) 1](#)).
- If a patient received more than the assigned IMP doses from study entry to DLT occurrence during the DLT assessment period, non-evaluability criteria will be reassessed by Sponsor and investigator ([Table \(2.1\) 1](#)).

Table (2.1) 1 - Minimum number of S64315 and azacitidine doses to meet minimum exposure until the end of cycle 1

Schedule description	Minimum of doses of S64315/azacitidine
S64315 during the 2-week LID period (LID1 on D-13 and LID2 on D-6)	2 out of 2
S64315 (D2, D9, D16 and D23 in 28-day cycle)	3 out of 4
azacitidine (D1 to D7 in 28-day cycle)	5 out of 7

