3.2.5. Treatments of patients

3.2.5.1. Extent of treatment exposure and treatment compliance

Details concerning definition on extent of exposure, treatment compliance are provided in [Appendix 4.2.1.5](#).

For S64315 and azacitidine separately the frequency distribution (n, %) or descriptive summary statistics (n, mean, SD, median, min, max, median, Q1, Q3) as applicable will be provided in

patients of the SS by planned dose level combination and overall for variables measured on a nominal scale according to the following classes:

- Extent of exposure*:
 - The global treatment duration (combined measure for S64315/azacitidine): summary statistics.
 - Treatment duration (weeks) overall and by treatment period (LID/Combination treatment).
 - Treatment duration (weeks) during combination treatment period (i.e., excluding LID) (< 4 weeks, [4-12[weeks, [12-24[weeks, [24-36[weeks, [36-48] weeks, >48 weeks).
 - LID duration ([0-1] week, [1-2] weeks and > 2 weeks).
 - Number of cycles (1 cycle, 2 cycles, 3-6 cycles, 7-10 cycles, > 10 cycles) during the combined treatment period.
 - Number of patients by cycle (LID, Cycle 1, Cycle 2, etc).
- Treatment compliance*:
 - Cumulative dose (mg) for S64315/ Cumulative dose (mg/m²) for azacitidine overall, by cycle (including LID), and for combination treatment.
 - Dose intensity (DI) (mg/week) for S64315/ DI (mg/m²/day) for azacitidine overall, by cycle (including LID), and for combination treatment.
 - Relative Dose Intensity (RDI) (%) for S64315/azacitidine overall, by cycle (including LID), and for combination treatment.
 - RDI for S64315(< 35%, [35-65[%, [65-100[%, ≥ 100%) overall, by cycle, and per treatment period (LID/Combination treatment).
 - RDI for azacitidine (< 62%, [62-85[%, [85-100[%, ≥ 100%) overall, by cycle, and per treatment period (Combination treatment).
 - Treatment interruption (Yes/No) during treatment period (including LID).
 - Reason of treatment interruption (Medical reason, Non-medical reason, Missing).
 - LIDLIDNumber of cycles with at least one treatment interruption for S64315 during treatment period (including LID).
 - Number of cycles with at least one treatment interruption for azacitidine during treatment period.
 - Cycle delayed (Yes/No) during treatment period (including LID).
 - Reason for cycle delayed (Medical reason, Non-medical reason, Missing).
 - Number of cycles delayed during treatment period (including LID).

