The dose intensity (*mg/ week*) for S64315 per cycle is defined as the cumulative dose (mg) received during the cycle divided by the cycle duration in weeks.

$$DI \left(\frac{mg}{wk} \right) \text{ at cycle } i = \frac{\text{Cumulative dose (mg) received at cycle } i}{\text{Duration of cycle } i \text{ (weeks)}}.$$

The duration of the last cycle will be estimated to be (*) weeks.

(*): 4 weeks for regimen QW, 2 week for LID.

Relative dose intensity (RDI) for S64315

The RDI (%) for S64315 per patient measures the percentage of the total trial dose planned that was really administered. It is defined as the ratio of the dose intensity (mg/week) to the initial planned dose intensity (mg/week)

$$RDI \text{ (%) per patient} = \frac{DI \text{ (mg/wk)}}{\text{Planned dose intensity (mg/wk)}} * 100.$$

The RDI (%) for S64315 per cycle is defined as the ratio of the dose intensity (mg/week) at cycle *i* (including LID cycles) to the planned dose intensity (mg/week).

$$RDI \text{ (%) at cycle } i = \frac{DI \text{ at cycle } i \text{ (mg/wk)}}{\text{Planned dose intensity at cycle } i \text{ (mg/wk)}} * 100.$$

Treatment interrupted for S64315

A treatment interruption is defined according to the S64315 infusion e-CRF page (Did the patient receive the IMP infusion (Yes/No)).

Number of cycles with at least one treatment interruption for S64315 experienced by a patient over the treatment period will be calculated.

Cycle delay for S64315

A cycle delay is defined according to the S64315 infusion e-CRF page (infusion postponed (Yes/No) at D2 of the cycle *i* or of LID2). Moreover, a delay of LID2 will be also considered if the duration of the LID1 is higher than 7 days, while a delay of cycle *i* will be also considered if the duration of the cycle *i-1* is higher than (*). In case of missing cycle delay reason, reason of cycle delay will be considered as unknown. The delay in days will be derived, based on the dates of administration.

Delay (days) of cycle *i* = (first IMP intake of cycle *i*) – (first IMP intake of cycle *i-1* + *x* days).

(*): 30 days for regimen QW (theoretical cycle duration + 2 days for potential technical or logistical difficulty). In the delay duration formulae above *x*=30.

(*) *x*=16 days if Cycle *i-1* is the LID period.

Number of cycles delayed for S64315 experienced by a patient over the treatment period will be calculated among patients experiencing a cycle delay.

Dose modification for S64315

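### As written, overall S64315 relative dose intensity falls with assigned dose even when every infusion is given, and the azacitidine interruption flag can miss partly dosed cycles

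*SAP*

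**What the plan says.** **S64315.** SAP 4.2.1.5 defines dose intensity per patient as "cumulative dose (mg) received during the treatment period divided by the total treatment duration in weeks, including LID period". For RDI per patient it says: "It is defined as the ratio of the dose intensity (mg/week) to the initial planned dose intensity (mg/week"). The same paragraph states that this quantity "measures the percentage of the total trial dose planned that was really administered". The planned values are in a table headed "4 intakes per cycle / 1 intake per LID week", with rows of 25, 50, 100, 200 and 250 mg/week. The 25 and 50 mg rows are footnoted as the two lead-in doses. The per-cycle RDI formula uses a planned value specific to that cycle; the per-patient formula does not.

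SAP 3.2.5.1 tabulates these measures in "patients of the SS by planned dose level combination and overall". S64315 RDI is put into four classes (below 35%, 35 to below 65%, 65 to below 100%, 100% or more), shown "overall, by cycle, and per treatment period (LID/Combination treatment"). Under SAP 2.1, "Patients who only received LID will be analysed according to the dose of S64315 planned to be administered".

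**Azacitidine.** The S64315 interruption item is "Did the patient receive the IMP infusion (Yes/No"). The azacitidine item instead asks whether the patient received at least one injection. Interruption days are scheduled days without an injection, but they are computed only in patients who have an interruption.

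**The concern.** The lead-in is fixed at every dose level, so its 75 mg and two weeks enter the S64315 numerator whatever dose the patient was assigned. Dividing by the assigned weekly dose then penalises patients in proportion to how far that dose exceeds the lead-in. A measure meant to show compliance would fall as dose level rises even when nobody misses an infusion.

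For azacitidine, an item that one injection is enough to satisfy cannot detect a partly given course, and the restriction on interruption days carries the gap into a second table.

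SAP 1.2 lists dose interruptions and dose intensity among the endpoints of the primary objective. Efficacy will not be analysed, so exposure and safety make up most of the report. A reader comparing dose levels could take the fall in RDI for poorer tolerability at higher doses.

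**Working it through.** The SAP gives no expected overall RDI to reproduce. Its planned values do agree with its schedule: 4 × D / 4 weeks = D mg/week for S64315, and 75 × 7 / 28 = 18.75 mg/m²/day for azacitidine.

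**S64315 inputs**
- Lead-in: 25 mg on D-13 and 50 mg on D-6, 75 mg in total (SAP 1.3.1).
- Combination period: assigned dose D on D2, D9, D16 and D23 of each 28-day cycle (SAP 1.3.1).
- Duration: last infusion + 6 days − first infusion + 1 (SAP 4.2.1.5). For one full cycle with no Day 0, D-13 to D29 is 13 + 29 = 42 days, or 6 weeks.

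With every due infusion given on schedule over w weeks (w ≥ 2) and D as denominator:

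RDI = (75 + (w − 2)D) / (wD)

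| Stopping point | w | 25 mg | 50 mg | 100 mg | 200 mg | 250 mg |
|---|---|---|---|---|---|---|
| Lead-in only | 2 | 150% | 75% | 37.5% | 18.8% | 15% |
| After C1D9 | 4 | 125% | 87.5% | 68.8% | 59.4% | 57.5% |
| One cycle | 6 | 116.7% | 91.7% | 79.2% | 72.9% | 71.7% |
| Two cycles | 10 | 110.0% | 95.0% | 87.5% | 83.8% | 83.0% |
| Six cycles | 26 | 103.8% | 98.1% | 95.2% | 93.8% | 93.5% |

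The one-cycle end points are 275/6 = 45.8 mg/week, /50 = 91.7%, and 1075/6 = 179.2 mg/week, /250 = 71.7%. If a Day 0 is counted (43 days), they become 89.5% and 70.0%.

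*No other table row repairs this.* One fully dosed cycle gives 29.2, 45.8, 79.2, 145.8 or 179.2 mg/week at the five levels, and none of these is a row of the table.

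*Ranking.* A 50 mg patient who missed D9 or D16 of cycle 1 has (75 + 150)/6 = 37.5 mg/week, /50 = 75.0%. That is above the 71.7% of a 250 mg patient who missed nothing.

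*Classes.* Stopping after C1D9 with no dose missed puts 50 and 100 mg in the 65–100% class but 200 and 250 mg in the 35–65% class. At 50 mg and above, an on-schedule, fully dosed patient cannot reach the top class.

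**Azacitidine**

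Take one cycle with injections on D1–D4 only.
- Duration: (4 + 21) − 1 + 1 = 25 days.
- Dose intensity: 4 × 75 / 25 = 12.0 mg/m²/day.
- RDI: 12.0 / 18.75 = 64.0%.
- Three scheduled days were missed, and the patient is below the 5-of-7 minimum exposure in SAP 2.1.
- If the item is asked once per cycle, the answer is Yes, so no interruption is flagged. The three days are not counted unless another cycle was missed entirely.

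**The case against.** **The S64315 denominator is undefined rather than wrong.** The table heading mentions lead-in weeks, its footnotes mark the lead-in doses, and the stated purpose of RDI refers to the whole planned trial dose. A sponsor could have meant a lead-in-weighted value, which would remove the problem. That is fair as to intent, but no such value is written anywhere, and the per-patient formula lacks the period-specific term that the per-cycle formula has. Two programmers could report 71.7% and 100% for the same patient.

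**The effect is small.** RDI by combination cycle and for the combination period does not involve the lead-in and is shown beside the overall value. The class shift among levels of 50 mg and above is gone by C1D16 (75.0%, 67.5% and 66.0% at 100, 200 and 250 mg), except that lead-in-only and other very early stoppers remain affected. The documents do not say which levels were tested. All of this stands and limits the weight of the point.

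**The azacitidine part depends on an eCRF page that is not in the documents.** This also stands. The at-least-one wording, and the reference in SAP 4.1.2 to first and last intake dates of azacitidine cycles, favour a per-cycle item without proving it. Days dosed and azacitidine RDI would still show the missed injections. DLT evaluability uses dose counts, not this flag.

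**Conclusion.** The concern holds, each part under its stated condition.

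With the assigned level as denominator, overall S64315 RDI under full dosing depends on dose level. After one cycle the gap between 50 and 250 mg is 91.7 − 71.7 = 20 percentage points; after six it is 98.1 − 93.5 = 4.6. This conflicts with the SAP's own description of RDI. The figures assume on-schedule dosing and no Day 0; counting a Day 0 changes the level slightly but not the direction.

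If the azacitidine item is recorded per cycle, only a cycle with no injection counts as interrupted.

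No decision rule uses either quantity, so this should be corrected before the tables are produced but does not threaten the trial's conclusions.

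**What to change.** 1. **S64315 overall RDI.** Divide the cumulative dose received by the dose planned over the patient's own w weeks: 25 mg for week 1, 50 mg for week 2 and D for each later week. This is the same as a planned intensity of (75 + (w − 2)D)/w for w of at least 2. If death or withdrawal cuts the last week short, count the full infusion due in the started week. For example, death two days after C1D9 at 250 mg gives 24 days (3.43 weeks). A prorated last week would give 133%, whereas counting the infusion due gives 575/575 = 100%. Full dosing then gives 100% at every level and stopping point. With one mid-cycle infusion missed in a single cycle, 50 mg gives 225/275 = 81.8% and 250 mg gives 825/1075 = 76.7% (55.0% under the present rule). Alternatively, drop the overall row and report the lead-in and combination periods separately, with 75/2 = 37.5 mg/week as the planned value if the lead-in is treated as one two-week period.

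2. **Azacitidine interruption.** Flag a cycle when any scheduled D1–D7 injection is not given while the patient is still on treatment (not after death or permanent discontinuation). Compute interruption days in all azacitidine-treated patients.

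The cost is SAP wording and derivation code. No new data are needed if injection dates are recorded, which the SAP's days-dosed derivation already assumes; this should be confirmed against the eCRF. If the sponsor already intended a weighted denominator or a per-injection item, one clarifying sentence for each is enough on those points.
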